3 OBJECTIVES AND ENDPOINTS

Objectives	Endpoints
Primary	

• To assess whether pre-ET changes an individual's preference for adjuvant radiation treatment• To assess whether pre-treatment with endocrine therapy changes the surgical oncologist's preference for adjuvant radiation treatment	
• Radiation preference question for participant pre and post pre-ET treatment• Radiation preference question for the surgical oncologist pre and post pre-ET treatment
Secondary	

• To obtain preliminary estimates to assess whether patient reported outcomes during pre-ET are predictive of long-term adjuvant endocrine therapy adherence• For those participants who agree to a radiation oncologist consultation, to assess whether pre-treatment with endocrine therapy changes the radiation oncologist's preference for adjuvant radiation treatment	
• PRO assessments• Radiation preference question for the radiation oncologist pre and post pre-ET treatment
Exploratory	

• To obtain preliminary data on the effect of pre-ET on decision outcomes for adjuvant therapy after BCS	
• PRO assessments
Exploratory	

• To obtain exploratory data on recurrence-free survival and overall survival	
• Recurrence-free survival and survival through 24 months

4 STUDY DESIGN

4.1 Overall Design

This is a multicenter study of pre-ET tolerance to inform treatment decisions for adjuvant radiation in geriatric individuals with early stage, ER⁺ breast cancer. Study therapy will include 90 days of pre-ET. Endocrine therapy options may include tamoxifen or AI (letrozole, anastrozole, or exemestane) and choice of endocrine therapy will be at the discretion of the treating physician. Following pre-ET, all individuals will undergo BCS. After BCS, enrolled participants and their physicians (surgical oncology, radiation oncology, and medical oncology) will finalize an adjuvant radiation and adjuvant endocrine therapy plan. Participants recommended for and accepting adjuvant RT will complete this as planned and then be recommended to re-start on adjuvant

Pre-Operative Window of Adjuvant Endocrine Therapy to Inform Radiation Therapy Decisions in Older Women with Early-Stage Breast Cancer

Version Date: 21 February 2023

endocrine therapy. Participants who do not have radiation will be recommended to restart on endocrine therapy after surgery. The choice and duration of adjuvant endocrine therapy will be determined by the treating medical oncologist. All participants regardless of their adjuvant therapy will be followed. Genomic profiling of the tumor may be performed if deemed clinically indicated by the treating medical oncologist and any recommended adjuvant chemotherapy will be completed prior to resumption of endocrine therapy in the adjuvant setting.

The primary objective is to assess whether pre-treatment with endocrine therapy changes an individual's or the surgical oncologist's preference for adjuvant radiation treatment. The secondary objective is obtain preliminary information to assess whether tolerance of pre-ET predicts adherence to adjuvant endocrine therapy.

Baseline assessment of patient beliefs and attitudes will be assessed using the Brief Illness Perception Questionnaire (BIPQ), the Beliefs about Medicines Questionnaire (BMQ) and BMQ Endocrine therapy subscale (BMQ ET), the Perceived Sensitivity to Medicine Scale (PSM), the Decision Regret Scale (DRS), and an additional novel survey of breast cancer and breast cancer medication specific patient beliefs.

Tolerance of pre-ET will be assessed using validated PRO assessments. Baseline and serial assessment of PROs will be conducted using the EORTC Quality of Life Questionnaire (QLQ-C30 and QLQ-BR23), the Breast Cancer Prevention Trial Symptom Checklist (BCPT-SCL), and the Center for Epidemiologic Studies Depression Scale Revised (CESD-R).

The Decision Regret Scale will be used to assess the effect of pre-ET on decision outcomes for adjuvant therapy after breast conservation surgery.

Adherence will be monitored throughout the endocrine therapy treatment period using patient report.

Up to 83 individuals will be enrolled.

4.2 Justification for Dose

Each of the endocrine therapy drugs will be used at standard doses described in the drug labels.

Radiation therapy will be completed in accordance with standard clinical practice.

4.3 End of Study Definition

Primary completion date is the date that the final participant is examined or receives an intervention for the purposes of final collection of data for the primary outcome, whether the clinical study concluded according to the pre-specified protocol or was terminated.

Study completion date is the date the final participant is examined or receives an intervention for purposes of final collection of data for the primary and secondary outcome measures and adverse events (for example, last participant's last visit), whether the clinical study concludes according to the pre-specified protocol or is terminated.

Collection and analysis of exploratory data may extend beyond the study completion date. The study may remain open with the IRB during this time.

5 STUDY POPULATION

5.1 Inclusion Criteria

In order to be eligible to participate in this study, an individual must meet all of the following criteria:

1. Provision of signed and dated informed consent form
2. Stated willingness to comply with all study procedures and availability for the duration of the study
3. ECOG performance status 0-2
4. Females, aged ≥ 65 years
5. Diagnosed with anatomic stage I, ER positive, PR positive or negative, and HER2 non amplified invasive breast cancer and clinically negative nodes; any invasive breast cancer histologic subtype may be enrolled
6. Tumor size ≤ 2 cm
7. Patient has elected BCS as surgical choice
8. Eligible to receive tamoxifen or an aromatase inhibitor
9. Ability to take oral medication and be willing to adhere to the endocrine therapy for the 3 month period prior to BCS
10. Agreement to adhere to Lifestyle Considerations (see [Section 5.4](#)) throughout study duration

5.2 Exclusion Criteria

An individual who meets any of the following criteria will be excluded from participation in this study:

1. Prior or current use of endocrine therapy for breast cancer
2. History of ipsilateral breast radiation
3. Pregnancy or lactation
4. Has a known additional malignancy that is progressing or requires active treatment. Exceptions include basal cell carcinoma of the skin or squamous cell carcinoma of the skin that has undergone potentially curative therapy or in situ cervical cancer.
5. Current or planned use of a strong CYP2D6 inhibitor (e.g. Fluvoxamine, Paroxetine) and is not able to receive an endocrine therapy agent that does not use the CYP2D6 pathway.

5.3 Justification for Study Population

Each year, nearly half of newly diagnosed breast cancer cases are in women 65 years and older. Recent data from randomized controlled trials have shown that omission of adjuvant radiation following BCS does not result in a decreased survival in women 65+ years old with estrogen receptor (ER) positive, node negative, small (≤ 2 cm) breast cancers. Despite these findings and inclusion of criteria for omission of radiation in NCCN guidelines, studies show that RT is still frequently used after BCS in this population⁵⁻⁷. Without patient-level data regarding tolerance to endocrine therapy physicians and patients are unable to make informed decision regarding omission of RT. This study is limited to women ≥ 65 years of age to develop treatment

Pre-Operative Window of Adjuvant Endocrine Therapy to Inform Radiation Therapy Decisions in Older Women with Early-Stage Breast Cancer

Version Date: 21 February 2023

recommendations that can be tailored to specific geriatric considerations. On the basis that the initial studies supporting the omission of radiation in the geriatric population were conducted in women and that the surgical plans and side effect profiles from endocrine therapies differ between men and women, men will be excluded from this initial pilot study.

5.4 Lifestyle Considerations

Individuals will be educated on potential interactions between the endocrine therapies and other drugs. The prescribing information will be referenced by the treating physician to identify potential interactions. If a potential interaction exists (e.g. use of another strong CYP2D6 inhibitor with the use of tamoxifen), alternative endocrine therapies may be considered for the individual or the individual may be prescribed an alternative CYP2D6 inhibitor for the treatment of other conditions.

5.5 Screen Failures

Screen failures are defined as participants who consent to participate in the clinical trial but are not entered in the study. A minimal set of screen failure information is required to ensure transparent reporting of screen failure participants, to meet the Consolidated Standards of Reporting Trials (CONSORT) publishing requirements (for NIH studies) and to respond to queries from regulatory authorities. Minimal information includes demography, screen failure details, eligibility criteria, and any serious adverse events (SAEs).

5.6 Strategies for Recruitment and Retention

Potentially eligible participants will be identified by treating clinicians. Participants who are interested in participating will have a consultation with a medical oncologist to discuss pre-ET.

6 STUDY INTERVENTION

6.1 Description of Study Intervention(s)

6.1.1 Endocrine Therapy

The choice of endocrine therapy will be determined by the medical oncologist. All endocrine therapy drugs are commercially available and will be prescribed at doses consistent with those described in the product label.

On the basis of the following criteria, the principal investigator has determined that the study meets the criteria for IND exemption.

- 1. The study is not intended to support FDA approval of a new indication or a significant change in the product labeling.**
The present study is not intended to get a new FDA approval for any of the included endocrine therapy drugs.
- 2. The study is not intended to support a significant change in the advertising for the product.**
The present study is not intended to result in a change in the advertising for any of the included endocrine therapy drugs.

Pre-Operative Window of Adjuvant Endocrine Therapy to Inform Radiation Therapy Decisions in
Older Women with Early-Stage Breast Cancer

Version Date: 21 February 2023

3. The investigation does not involve a route of administration or dosage level or use in a patient population or other factor that significantly increases the risks (or decreases the acceptability of the risks) associated with the use of the drug product.

Each of the included endocrine therapy drugs within the present study will be used at standard dosing, route of administration and schedule as indicated in the package inserts. The only change of use from the label is that the endocrine therapy will be administered as 3 months of pre-ET in addition to adjuvant therapy recommended for at least 5 years. While the endocrine therapy labels do not include pre-ET use, there is sufficient clinical evidence in the literature documenting the safety of pre-ET in hormone receptor positive breast cancer. This has been prospectively studied and deemed to be an appropriate treatment approach in selected patients. Based on these studies, the NCCN Breast Cancer guidelines include a line stating that “Neoadjuvant endocrine therapy alone may be offered to those with strongly hormone receptor-positive tumors.” It is the investigator’s opinion that three months of pre-ET does not result in increased risk to the targeted patient population of ER positive breast cancer patients.

4. The study is conducted in compliance with institutional review board (IRB) and informed consent regulations set forth in parts 56 and 50 (21 CFR parts 56 and 50).

The present study is submitted for internal review by both the Protocol Review Committee and the IRB and will be monitored closely.

5. The study is conducted in compliance with § 312.7 (promotion and charging for investigational drugs).

The present study is conducted in compliance with promotion and charging for investigational drugs.

6.1.2 Radiation Therapy

Radiation therapy will be administered in accordance with standard clinical practice.

6.2 Dosing and Administration

6.2.1 Endocrine Therapy

The dosing and administration of endocrine therapy will be in accordance with the drug label for each drug prescribed by the medical oncologist.

Individuals will not switch endocrine therapies during pre-operative endocrine therapy; however, an individual may stop endocrine therapy at any time during pre-operative therapy. Individuals who stop neo-adjuvant therapy prior to 90 days may still be eligible to receive adjuvant endocrine therapy.

Individuals may take different endocrine therapies during neo-adjuvant and adjuvant therapy.

Pre-Operative Window of Adjuvant Endocrine Therapy to Inform Radiation Therapy Decisions in Older Women with Early-Stage Breast Cancer

Version Date: 21 February 2023

Individuals may also switch endocrine therapies (e.g. switch from an aromatase inhibitor to tamoxifen) during adjuvant therapy.

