2.2.4 Adherence to Endocrine Therapy in the Geriatric Population

Adherence to endocrine therapy in clinical practice is low. Non-adherence to endocrine therapy as documented in large adjuvant endocrine therapy trials is estimated between 23-28%, but it is even higher in studies examining non-adherence in clinical practice^{8,9}. A systematic review of adherence to adjuvant endocrine therapy in clinical practice shows that adherence at 5 years ranges from 32 -73%. Within this systematic review, reports of 5-25% of women on AIs discontinued treatment within the first two years⁹. At year 5, 47.1% of patients discontinued tamoxifen and 31.3% discontinued AI treatment²⁶. Non-adherence to adjuvant endocrine therapy results in increased recurrence and mortality²⁷. Capturing reasons for non-adherence is challenging with studies often reporting on demographic factors, but not identifying patient experience factors such as tolerability of the medication or a patient's perception of risk and benefit of therapy. Demographic factors identified as predictive of non-adherence include younger age, type of surgery (BCS), more comorbid conditions, and African American race²⁸.

There is a need to better define health related quality of life (HRQOL) and patient reported factors for non-adherence within clinical practice. Intolerable patient side effects is the most common patient reported reason for endocrine therapy non-adherence²⁹ with musculoskeletal symptoms being the primary reported toxicity leading to AI discontinuation^{26,30}. Musculoskeletal side effects are estimated to occur in up to 50% of patients on adjuvant AI treatment³¹. The Exemestane and Letrozole Pharmacogenetics (ELPh) trial was a multicenter, prospective randomized study comparing adjuvant exemestane and letrozole that included patient reported outcomes (PROs) and adherence data. Within this study, 32.6% of patients discontinued adjuvant AI (median follow up 15.5 months +/- 9 months) with the primary reason being musculoskeletal symptoms. Of the entire study population, 24.4% discontinued adjuvant AI because of musculoskeletal symptoms. The median time to treatment discontinuation was 6.4 months³².

2.2.5 Tolerance as a Predictor of Non-Adherence to Endocrine Therapy.

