8.1.1 Exams and Evaluations

The following will be performed by a licensed clinician:

- Medical History
- Physical Exam -Breast exam and axillary lymph node exam.
- Vital signs (pulse, blood pressure)
- Start and stop dates of pre-ET and adjuvant endocrine therapy; reason for discontinuation

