10.3 Sample Size Determination

Sample size estimation is based upon accruing a sufficient number of participants to assess the primary objective separately for participants and surgical oncologist responses with an overall one-sided 10% type I error rate (5% for each individual test). Accrual of 70 evaluable participants provides 90% power to test for a change in adjuvant radiation treatment preference between the pre-op visit and on-study in the participant study population from a null difference of 5% to an alternative of at least 15% with a target one-sided 5% level binomial test (by exact enumeration). Accrual of 70 evaluable participants also provides 90% power to independently test for a change

Pre-Operative Window of Adjuvant Endocrine Therapy to Inform Radiation Therapy Decisions in Older Women with Early-Stage Breast Cancer

Version Date: 21 February 2023

in adjuvant radiation treatment preference of the surgical oncologist between the pre-op visit and on-study in the participant study population from a null difference of 5% to an alternative of at least 15% with a one-sided 5% level binomial test. For fixed target size and power, the detectable difference increases from 10% to 15% when the assumed null varies within the expected range of 5% to 20%.

This is a pilot study to obtain preliminary data to estimate which if any PRO measures are associated with adherence to post-operative endocrine therapy. With n=70, a logistic regression of the dependent variable of adherence or not to endocrine therapy by year 2 on a continuous PRO measure score achieves 80% power at a 5% significance level to detect an odds ratio of 2 when the probability of adherence is 25%. These error rate estimates assume no adjustment for multiple comparisons among the different PRO.

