10.4 Accrual

Maximum target sample size is estimated at 83 eligible participants which adjusts for a 15% lost to follow-up/dropout rate. In 2018 and 2017, 70 and 78 patients, respectively, met the basic inclusion criteria at UVA. Assuming 60% of future patients will agree to enroll in the study, target accrual to the study should be achieved in less than two years.

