10.5.2 Analyses

Primary analyses will not adjust for center. Summary measures will be described overall and by center. Demographics and baseline characteristics will be described for all study participants. Characteristics to be examined include: race/ethnicity, age, performance status, stage, ER, PR and HER-2 status, histologic subtype, tumor size date of diagnosis.

Adverse events will be coded based upon the NCI CTCAE v5.0. Safety will be reported by frequency and severity of adverse events.

The primary analysis will be based upon responses from a) study participants and b) surgical oncologists to the radiation questions, separately, without adjustment for center. For each response group, the proportion of responses that differ from the pre-op visit compared to the on-study (baseline) response (yes to no; or no to yes) will be calculated along with 95% confidence intervals. For each group, we will test that pre-ET resulted in a change in preference for adjuvant

Pre-Operative Window of Adjuvant Endocrine Therapy to Inform Radiation Therapy Decisions in Older Women with Early-Stage Breast Cancer

Version Date: 21 February 2023

radiation therapy in more than 10% of participants compared to no change with a one-sided 5% level exact binomial test.

Graphical methods will be used to display the PRO outcomes over time. On the most basic level, logistic regression models with adherence to post-op endocrine therapy at 2 years as the dependent outcome and the range of PRO measurement as independent factors will be used to obtain initial estimates of the predictive value of the protocol defined PRO to determine adherence. Other exploratory repeated measures models will be explored to determine if changes over time are also associated with determination of non-adherence. Exploratory analyses could include the assessment of PRO for quality adjusted life years or healthy-year equivalents. In all exploratory models, individual or simultaneous associations will be deemed promising for factors with $p < 0.1$.

The secondary analysis related to the radiation oncologist's preference will be based upon the subset of pre and post pre-ET responses from for the consulting radiation oncologist. The proportion of responses that differ from the pre-op visit compared to the on-study (baseline) response by at least one point (in either direction) will be calculated along with a 95% confidence interval.

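### The two-year adherence models pool tamoxifen and aromatase inhibitor users without a drug-class term, so estimates for PROs measured during pre-operative therapy can be biased in either direction

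*Combined protocol and SAP*

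**What the plan says.** Section 4.1 leaves the choice between tamoxifen and three AIs to the treating physician. Section 6.2.1 forbids a switch during pre-operative endocrine therapy (pre-ET), but then says "Individuals may take different endocrine therapies during neo-adjuvant and adjuvant therapy" and also allows switching during the adjuvant period.

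For the adherence objective, section 10.5.2 plans logistic regressions of two-year adherence in which "the range of PRO measurement as independent factors will be used". No drug or class term, stratum or subset is named. The analysis population in section 10.5.1 is not split by drug, and drug is not among the characteristics that section 10.5.2 lists for description. Section 8.1.1 records "Start and stop dates of pre-ET and adjuvant endocrine therapy; reason for discontinuation".

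The background in section 2.2.4 reports that at year 5 "47.1% of patients discontinued tamoxifen and 31.3% discontinued AI treatment". It also names musculoskeletal symptoms as the main toxicity behind stopping an AI. The trial cited in sections 2.2.4 and 2.2.5 as evidence that early PROs predict discontinuation compared two AIs and had no tamoxifen arm.

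The power statement in section 10.3 reads "With n=70, a logistic regression of the dependent variable of adherence or not to endocrine therapy by year 2" on a continuous PRO score "achieves 80% power at a 5% significance level to detect an odds ratio of 2 when the probability of adherence is 25" per cent. It adds that "These error rate estimates assume no adjustment for multiple comparisons among the different PRO".

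**The concern.** A variable that affects both predictor and outcome distorts their crude association. By the protocol's own background, drug class is such a variable: it shapes which symptoms a woman reports during pre-ET, and it is associated with how often she stops.

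For a score that is worse on AIs, such as the musculoskeletal cluster, the women with higher scores belong more often to the class with lower discontinuation, and the pooled estimate is pulled toward no association. For a score that is worse on tamoxifen, the pull is the other way. Separately, a woman who restarts on another drug carries a pre-ET score that describes a drug she no longer takes, which may weaken the association.

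At stake is the reading of a named secondary objective. Its estimates are meant to feed a tool whose scope, in section 2.3, includes the choice of endocrine therapy.

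**Working it through.** **1. The plan's own power figure.** Inputs from section 10.3: n = 70, odds ratio (OR) 2 (taken per SD of the score, as the unit is not stated), P = 0.25, 5% level (sidedness not stated for this model). For one continuous covariate,

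power = Φ( ln(OR) × √[n P(1−P)] − z ).

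Here √(70 × 0.1875) = 3.62 and ln 2 = 0.693, product 2.51.

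- One-sided 5% (z = 1.645): 80.7%.
- Two-sided 5% (z = 1.960): 70.9%.

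The stated 80% reproduces if the test is one-sided. The rarer outcome group has 70 × 0.25 = 17.5 women.

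**2. Class and discontinuation (section 2.2.4).** Tamoxifen odds 0.471/0.529 = 0.890; AI odds 0.313/0.687 = 0.456; ratio 1.95. This is a year-5 figure, whereas the model is at year 2.

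**3. Size of the confounding.** Large-sample simulation of

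logit P(discontinue) = a + ln(2)·X + ln(1.95)·T,

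where T = 1 for tamoxifen, X has SD 1 within class and a mean shifted by class, and a gives 25% discontinuation overall. A logistic model in X alone is then fitted. The tamoxifen share and the shift are assumptions, because the documents give neither. So is holding 1.95 at equal PRO score.

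| Scores worse on | Shift | 10% tamoxifen | 30% | 50% |
|---|---|---|---|---|
| AIs | 0.5 SD | 1.92 | 1.85 | 1.82 |
| AIs | 0.8 SD | 1.90 | 1.80 | 1.76 |
| Tamoxifen | 0.8 SD | 2.10 | 2.19 | 2.23 |

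The within-class OR is 2.0 throughout. At 1 SD worse on AIs with 50% tamoxifen, the pooled OR is about 1.7. Solving the large-sample equations directly agrees with these values to within 0.02. With a true OR of 1.0 and shifts of 0.3 to 0.8 SD in either direction, the pooled OR lies between 0.89 and 1.12.

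**4. Dilution by drug change, as illustration only.** With a share s on a different adjuvant drug, an approximation is

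ln(pooled OR) = (1−s)·ln 2 + s·ln(OR in changers).

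The documents give neither s nor the OR in changers.

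| OR in changers | s = 10% | 30% | 50% |
|---|---|---|---|
| 1.0: pooled OR (one-sided power) | 1.87 (73%) | 1.62 (55%) | 1.41 (35%) |
| 1.4: pooled OR (one-sided power) | 1.93 (77%) | 1.80 (68%) | 1.67 (59%) |

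**5. Cost of a class covariate.** Replace n by n(1−R²), where R² is the squared correlation of score and class. For assumed R² of 0.02 to 0.15, one-sided power goes from 80.7% to between 80.0% and 74.9%, and two-sided power from 70.9% to between 70.1% and 63.9%. That is roughly 1 to 7 points. In the most extreme case of step 3 (1 SD, 50% tamoxifen), R² = 0.25/1.25 = 0.20, and power would be 72.6% one-sided or 61.3% two-sided.

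**The case against.** **The aim is prediction in a pilot.** Physician-chosen drugs and later switches belong to the setting where a tool would be used, and whether tolerance of the drug tried predicts staying on any endocrine therapy is a fair pooled question. This stands, and it is why the unadjusted estimate should be kept. It does not remove the need for the adjusted one: a pooled estimate depends on this trial's drug mix and may not carry over to another. Section 10.5.2 leaves room for further exploratory models but commits to no drug term in any of them.

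**The mechanism depends on when the PRO is measured.** Section 10.2 names pre-treatment PROs and section 10.5.1 requires on-study PROs. A footnote to the schedule in Appendix 1 has the surveys completed before the first dose, so the drug cannot have affected those scores. This stands and limits the point to PROs taken during pre-ET, which is how section 3 words the objective.

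**Stronger readings that the documents do not support.**

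- A reader might infer that the bias runs toward the null. That holds only for scores that are worse on AIs. The PROs in section 8.2.3 also cover vasomotor, vulvovaginal, mood, cognitive, depression and quality-of-life domains.
- A reader might infer a larger distortion by treating 1.95 as the class OR without holding the score fixed. At 50% tamoxifen and a 1 SD shift, the pooled OR is then about 1.46, but this implies a class OR of about 4.1 at equal score, which nothing in the documents supports.
- A reader might infer that switching sharply cuts power because poor tolerators change drug and their first score tells nothing about the second drug. No section states either premise.
- A reader might infer that switchers would be counted as non-adherent. The question in Appendix 10 asks about hormone treatment in general, so a woman who takes a new drug daily would answer as taking it.

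**Conclusion.** The point holds as a limited weakness in a secondary analysis. The planned models omit a variable that the protocol itself ties to both sides of the association, so estimates for PROs measured during pre-ET can be off in either direction. In the range tried, a true OR of 2.0 is displaced to between about 1.7 and 2.2, which is modest. That range rests on assumed drug shares, assumed score differences, and a year-5 class OR applied at equal score to a two-year outcome. Dilution by later drug changes is possible and could be larger, but the documents do not allow it to be sized. The documents also do not support the inference that the trial would wrongly declare tolerance uninformative: the models are labelled preliminary, and no rule turns a null estimate into that conclusion. The primary radiation-preference tests do not use these models.

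**What to change.** In section 10.5.2:

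- Add pre-ET drug class (AI or tamoxifen) as a covariate in the adherence models that use PROs measured during pre-ET, and report the unadjusted estimate alongside.
- Tabulate drug by period (pre-ET and adjuvant).
- If an estimate in women who restart the same drug is shown, label it a sensitivity analysis. It selects on an event after treatment that may itself result from poor tolerance, and it reduces an already small number of events.

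The cost is a few lines of SAP text and one degree of freedom against about 17 to 18 events, or roughly 1 to 7 power points at an assumed R² of 0.02 to 0.15. Sample size and the primary analysis do not change.
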